Data on staffing in the CLCs will be obtained from VA's Corporate Data Warehouse (CDW) accessed through VINCI and stored locally on the secure research server in the designated restricted study drives through an existing DART request. This will be used to characterize the intervention and control CLCs in terms of the level of skilled and unskilled staffing at each CLC. This will help us to interpret the results of the comparison of hospitalization rates from the CLCs.

Residential History File (RHF): [name] and colleagues have constructed algorithms that concatenate the MDS and Medicare Claims files into individual patient histories able to document trajectories as patients move in and out of hospital and other settings. Continuous days of health care utilization at the same health care location are assigned in calendar time. In the case of overlapping dates, a hierarchy (inpatient claims, SNF, hospice, and home health) is used to assign location of care. Prior experience has found that very few claims have overlapping dates of service (less than 0.05%), reflecting the ongoing error checking CMS does. More recently, under a current VA IIR, [name] has applied the RHF to the combined VA-Medicare data, making it possible to track daily health care utilization of Veterans. This algorithm makes it possible to count the number of patient days at risk of hospital admission amongst residents in a CLC during any period of time. It is this feature of the RHF that makes it possible for us to precisely measure hospitalization rates in this study.

Implicit Review of Potentially Avoidable Hospitalizations: To estimate whether the rates of avoidable and inappropriate transfers changed with implementation of INTERACT, we will conduct a Structured Implicit Review (SIR) of the appropriateness of a sample of hospitalizations drawn from the CLCs participating in the intervention. To account for the heterogeneity and complexity of the CLC populations between sites, as well as the wide variety of factors that may influence the transfer decision, we will use SIR methodology to measure the appropriateness of transfer. SIR specifies key data sources for review and guides reviewers to consider specific domains in evaluating care. SIR has been shown to have acceptable reliability where data elements have not been specified in a manner that fully supports explicit reviews and where consideration of care elements requires clinical synthesis.[5]

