[name] will assist the research team in recruiting up to 17 reviewers experienced with CLC care from VA GRECC clinical staff and from VA CLC Medical Directors not working at CLCs involved in the implementation of INTERACT. We will use VA reviewers to facilitate credentialing and access to records. VA staff are more familiar with the VA population and the VA electronic health record. The expert reviewers will be carefully trained in the use of the SIR. [name] has experience in training clinical reviewers in performing SIR. Training will include reviewers independently completing a SIR on standardized practice charts. This will be followed by face-to-face meetings among reviewers to discuss their judgments and to clarify definitions and the information sources necessary to support a particular position viz. the potential "avoidability" of a hospitalization. Practice charts will be reviewed with the group discussion continuing until sources of disagreement have been resolved.

Reviewers will return to their facility where they will be assigned records to review from a nested random sample of the records of 163 residents transferred from the intervention facilities prior to the intervention compared to a nested random sample 163 residents transferred during the supported routine care phase (i.e. after the 6 month training period has been completed). Each reviewer will be asked to review up to 30 charts, each requiring between 45 and 75 minutes. During the initial review period, 25 charts will have a second review to determine inter-rater agreement in the current sample. We will conduct monthly calls with the reviewers to encourage completion of reviews and to clarify questions or issues arising during reviews.

CLC Selection, Matching and Random Assignment: We will match up to 15 pairs of CLCs to ensure at least 8 implement the INTERACT program. Prior to undertaking the facility matching process and in consultation with GEC officials, we may exclude facilities experiencing challenges or management problems that would make them poor intervention candidates. We may also exclude from the matching process CLCs that are atypical or have very high proportions of long stay Veterans with histories of psychiatric conditions, since this population of Veterans has a different profile than our target population and are likely to be hospitalized in an inpatient setting for drastically different reasons.

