An alternate version of the outcome is a ***per-person, risk adjusted, probability of hospitalization*** variable which will be calculated and compared across intervention and control CLC pairs. In 2007, 32% of Veteran's were hospitalized at any time during the course of the year, ranging from under 10% per CLC to nearly 50%. However, since each Veteran had a different number of person months of observation, something that varies across CLCs, these individual probabilities will be examined separately for short and long stay patients. For short stay patients, we'll calculate the proportion with a 30 day re-hospitalization, adjusting for patient characteristics on the admission MDS and the originating hospital diagnosis and length of stay. For long stay residents (those who are residents of a CLC for at least 100 days), we will calculate the likelihood of hospitalization over a 6 month period, adjusting for MDS measured clinical and functional characteristics relying upon the MDS assessment closest to the beginning of the 6 month period. Both of these measures have been extensively used in the literature using Medicare fee for service claims and have been used by [name] and his colleagues at Brown in preparing these measures for use in the Commonwealth Scorecard system to rate states' health care system.[2][[37]]

The underlying intent of the intervention is to decrease transfers by avoiding decline, appropriately managing acute change or decline in the CLC, and improving the use of advance care plans. Transfer rates alone do not tell us whether these kinds of changes occurred in association with the focused intention of the intervention, i.e. to reduce the rate of potentially avoidable hospitalizations. We will therefore also examine the overall rates of ***potentially avoidable and inappropriate transfers*** prior to the intervention compared to these rates during the consolidation phase of the intervention (among only the CLCs exposed to the INTERACT program), using a tested and reliable structured implicit review process. The Structured Implicit Review (SIR) yields numerous judgments about the need for transferring the Veteran to the hospital and attributes this decision to whether identifiable clinical care problems had been missed and the expected benefits of hospitalization. The final outcome variable is an ordinal variable ranking the hospitalization in terms of the degree of "avoidability".

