Using the results of the Structured Implicit Review process, we will determine the percent of hospital transfers rated as avoidable through better quality of preventive care and early change recognition and the percent rated as inappropriate because the Veteran’s condition could have been safely managed in an average VA CLC. We will compare the percentage hospitalized before the implementation to that after implementation. The sample size of 326 hospitalization records, 163 pre and 163 post-INTERACT, is based upon the assumption that the pre-intervention rate of potentially avoidable hospitalizations will be 40%. For the overall project, we are hypothesizing that there will be a 20% reduction in hospitalizations. Logically, the reductions in hospitalizations will come primarily from the "avoidable" type (otherwise we have a causal inconsistency). Thus, if 40 of 100 hospitalizations pre INTERACT are avoidable and all of the 20% reduction in hospitalizations (20 of 100) will come from among those that are avoidable, we expect a 50% reduction in the rate of avoidable hospitalizations. So, if the pre rate is 40% and the post rate is 20%, using a one tailed test at the alpha .05 level, we need about 100 records

before and 100 after to achieve a power of .90. In the event that some "unavoidable" hospitalizations are really avoided due to the intervention, we increase the sample size to 163 per time period.

Finally, we will test for unintended consequences by examining changes in the rates of overall mortality and in the rate of decline in the late loss ADLs, as measured by the MDS 3.0 nursing home resident assessment, which is done upon admission, periodically thereafter and upon discharge.[45]

Random selection of records with a transfer: A total of 326 medical records with a transfer to the hospital and across the eight intervention CLC sites will be reviewed, 163 pre-INTERACT intervention and 163 post-intervention.

The 163 pre-INTERACT records will be selected from a list of transfers that occurred during the 18 months prior to INTERACT being introduced to the CLCs. This list will be compiled by the study programmer/analysts who will pull it from current CDW data and MDS data. Once the list is generated, random selection will occur to obtain 163 records pre-intervention.

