restricted folder within the Providence VA Research Server and PKI encryption by email for this purpose throughout the process to do the reviews and share information with the research team, from Providence and LAVMC related to assistance with the SIR process.

The reviewers will complete each review using the SIR Instructions and Form (appendix 7). They will save each review to the secure designated restricted folder. If they choose to hand write their responses, they will scan the original review in and save on the secure restricted designated folder or send encrypted (PKI) to the project coordinator in Providence to be stored on the secure restricted folder within the Secure Providence VA Research Server. The original hand written copies will be stored locally in a designated locked location by the reviewer for the specified time frame noted in RSC-10.

While the reviewer will have access to complete medical records, only specific identifiable information from any medical record will be shared with the research staff (from Providence and LAVMC) to assist them in making sure they are accessing the correct record prior to their reviews. That information would include the Veterans name, Date of birth, last four of SSN, treatment dates being reviewed and the information contained in the Review Form (appendix 7).

REDCap may be used to input the reviews for analysis. The reviews would be input by Providence VA research team members, stripped of any identifying information and used to confirm the hypothesis that a reduction in avoidable hospitalizations was accomplished by the use of the INTERACT intervention, specifically the use of the SBAR change in condition progress note within CPRS. Review by the local privacy officer and local ISO confirms that the use of REDCap for the requested data is acceptable and within the guidelines of use.

REDCap is a secure data storage method. We will use this data storage option because it provides: 1) an intuitive interface for validated data entry; 2) audit trails for tracking data manipulation and export procedures; 3) automated export procedures for seamless data downloads to common statistical packages; and 4) procedures for importing data from external sources.

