Like all research studies, ours has various limitations. First, our design requires comparisons over time and between our intervention and control VAMCs under which we assume no other competing forces such as policy changes that might confound our interpretation. Secondly, we assume that reductions in hospitalization are desirable from the Veterans' perspective and that many of the current hospitalizations of Veterans from CLC are, indeed, avoidable. Third, we assume that CLCs offered the opportunity to introduce a new training program will be interested in doing so, which, given the strong interest in the private sector, we feel will actually occur. Fourth, we are explicitly treating the introduction of the INTERACT intervention as a quality improvement demonstration which CLCs and VAMC leadership can choose to adopt as an administrative practice rather than as research *per se*. Finally, as noted, it is likely that the intervention would be more smoothly implemented were its documentation features fully integrated into Veteran's medical record, but the complications and cost associated with such a significant local departure from the medical record system may be too great to be borne by a single research project.

Dissemination:

As part of the LTC CREATE, the INTERACT trial is embedded within a broader dissemination structure that has direct access to senior officials within the VHA who are committed to transforming the character of the VHA long term care system to be more Veteran centered and evidence based. This is described in detail in the accompanying CREATE overview. Our principle vehicle for dissemination is the Geriatric and Extended Care (GEC) service and the Office of Patient Centered Care and Cultural Transformation (OPCCCT). Every 6 months the LTC CREATE investigators will meet with GEC and, in consultation with them, determine which insight or finding from a LTC CREATE project will be highlighted and incorporated into a report that Planetree (currently a major contractor to OPCCCT helping to transform the VHA) prepares and which identifies examples of positive instances of transformation around the country. Thus, GEC leadership will be fully engaged in interpreting and then developing a practical implementation strategy for the findings of the INTERACT research program.

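### The avoidability chart review is an uncontrolled before-after comparison, so its result should be reported as an association and not as confirmation that INTERACT, or the SBAR note, caused the reduction

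*Combined protocol and SAP*

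**What the plan says.** Under Implicit Review of Potentially Avoidable Hospitalizations, the plan reviews "a sample of hospitalizations drawn from the CLCs participating in the intervention". Outcome Measures repeats the restriction: avoidable and inappropriate transfers are compared before and after "among only the CLCs exposed to the INTERACT program". Aim #4 fixes the sample at 163 transfers from the 18 months before INTERACT and 163 from afterwards, across the eight intervention sites. No control chart is sampled, and no adjustment for time trend is described for this outcome.

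The sizing rests on this case: "if the pre rate is 40% and the post rate is 20%, using a one tailed test at the alpha .05 level". For 90% power the plan arrives at roughly 100 charts in each period, and it then raises this to 163.

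The Structured Implicit Review (SIR) Procedure says that the reviews, once entered, will be "used to confirm the hypothesis that a reduction in avoidable hospitalizations was accomplished by the use of the INTERACT intervention", and it names the SBAR progress note specifically. The wording of Aim 4 is weaker: it asks whether the intervention was associated with fewer avoidable hospitalizations. For the primary hospitalization rate, by contrast, Aim #4 compares intervention CLCs with their matched controls by difference-in-differences.

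Limitations states for the design as a whole that "we assume no other competing forces such as policy changes that might confound our interpretation".

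**The concern.** A before-after comparison in exposed sites gives the effect of the intervention plus whatever else changed over the same period. Here that includes transfer practice, resident acuity and how charts are written. The plan itself makes background change plausible. The section on significance to the VHA presents INTERACT as one part of a wider effort to improve CLC care, and Aim #1 expects acuity to change and reports large increases over time in the Medicare fee-for-service system.

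The SBAR attribution is a further step. INTERACT introduces four types of tool together (communication, decision support, advance care planning, quality improvement). A comparison of two periods cannot credit one of them.

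This review is the plan's means, under Aim 4, of showing that the hospitalizations prevented were avoidable ones. If the causal sentence stands, a general decline in avoidable transfers would be reported as an INTERACT effect.

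**Working it through.** **1. Reproducing the stated sample size.** Inputs from Aim #4: 40% before, 20% after, one-sided alpha .05, power .90.

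- Uncorrected: n = [1.645·√(2·.30·.70) + 1.282·√(.40·.60 + .20·.80)]² / .20² = (1.066 + .811)² / .04, which rounds up to 89.
- With continuity correction: 98 per period. This agrees with the stated figure of about 100.
- At 163 per period, one-sided power is .99 for 40% against 20%.
- The plan's own reasoning removes 20 avoidable transfers from 100. That leaves 20 of 80, so the share among sampled post transfers is 25%. At 25%, power with 163 per period is .90.

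**2. What the uncontrolled test does under secular drift alone.** The drift sizes are assumptions; the documents give none for the avoidable share. With no INTERACT effect and a fall of d from 40%:

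z = d / √(2·p̄(1−p̄)/163), and the probability of significance is P(Z > 1.645 − z).

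| Assumed fall | p̄ | z | Probability of a significant result |
|---|---|---|---|
| 3 points | .385 | 0.56 | 14% |
| 5 points | .375 | 0.93 | 24% |
| 10 points | .350 | 1.89 | 60% |

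A difference-in-differences under a shared 10-point fall rejects in 5% of simulated trials (400,000 runs).

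**3. What control charts could add.**

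- Capacity: the plan gives ceilings of 17 reviewers and, in its words, "Each reviewer will be asked to review up to 30 charts". At both ceilings 17 × 30 = 510. Planned use is 326 + 25 second reviews = 351, which leaves 159, or about 79 control charts per period. With 15 reviewers 99 remain (450 − 351), with 13 reviewers 39, with 12 reviewers 9, and with 11 none.
- Power with controls flat at 40%, one-sided .05, intervention falling to 20%: SE = √(.40/163 + .48/79) = .092; .20/.092 − 1.645 = 0.52; power .70.
- Intervention falling to 25%: SE = √(.4275/163 + .48/79) = .093; .15/.093 − 1.645 = −0.04; power .49.
- Clustering: with 163/8 ≈ 20.4 charts per site and period, the design effect is 1 + 19.4·ICC. If it applied in full, .70 would become .63, .58 or .46 at assumed ICCs of .01, .02 or .05.
- Testing the control arm alone: with 79 + 80 charts and a real fall from 40% to 30%, SE = √(.35·.65·(1/79 + 1/80)) = .076, z = 1.32, and the chance of significance is 37%. For a 5-point fall it is 16%.
- Time: 159 reviews at 45 to 75 minutes is 119 to 199 hours, 45% more reviews than the 351 planned.

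**The case against.** The strongest reply is that this is an openly stated secondary comparison. The controlled test of INTERACT is the primary hospitalization rate, with matched pairs and difference-in-differences. Aim 4 speaks of association, its analysis text only compares percentages, and Limitations declares the assumption of no competing forces. The causal wording sits in one sentence about data entry. All of that stands, and it makes the repair mainly one of wording. It does not rescue the sentence, which states a conclusion the comparison cannot reach.

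Three stronger readings are tempting, and the documents do not support them.

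- *Every kind of drift is credited to INTERACT.* Pre and post charts are combined, put in random order, assigned at random and reviewed without a period label. Change in rater stringency is therefore largely balanced, and only secular change remains. SBAR notes in post charts may reveal the period, but control charts would not cure that.
- *The earlier INTERACT study shows how large the drift would be.* The 3% fall in its comparison homes and the 6% fall in its non-engaged homes are relative falls in all admissions, not in the avoidable share. Even if every lost admission had been avoidable, the share would move from 40% to 37/97 = 38.1% or 34/94 = 36.2%. The test would then be significant with probability of about 10% or 18%. The 5- and 10-point rows above have no source in the plan.
- *Reviewer slots are lying unused and controls are cheap.* The 159 slots exist only if two ceilings are both reached. The procedure divides the 326 charts equally, about 19 each with 17 reviewers. Chart access is arranged for the eight intervention sites only. Reviewers are barred from intervention CLCs but not from control CLCs, so own-site review would need a new rule that still keeps control status within the research team.

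**Conclusion.** The point holds in a limited form. The chart review has no control sample, so secular change in practice, case mix or charting cannot be separated from INTERACT, and the sentence claiming confirmation, with its SBAR attribution, goes beyond both the design and Aim 4. The size depends on a drift nobody knows: about 14%, 24% or 60% probability of a falsely significant result for assumed falls of 3, 5 or 10 points. These figures take charts as independent, as the plan's own calculation does.

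Adding control charts is a design option and not a required correction. At the most generous reading of capacity it gives power of about .49 to .70 before clustering, against the .90 the plan sought for the before-after test. A reader might also infer that a non-significant change in control charts would restore the causal claim. It would not, since a real 10-point control fall would be missed about 63% of the time.

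**What to change.** **Change.** In the Structured Implicit Review (SIR) Procedure, replace the causal sentence with wording such as:

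> *The reviews will be used to estimate the change, from before to after INTERACT, in the share of transfers judged avoidable in the intervention CLCs. There is no control sample, so the result will be reported as an uncontrolled association and will not be attributed to any single INTERACT tool.*

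Drop the attribution to the SBAR note, and use the same description wherever the chart review is reported under Aim 4. The cost is a text edit.

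**Optional, if reviewer numbers allow.** Add a random sample of transfers from the matched control CLCs, from the same calendar months, in the same masked list. The limit is about 79 per period, and only with 17 reviewers at 30 charts each. Report the difference-in-differences estimate with its interval as supportive, state its limited power, and do not read a non-significant control change as proof of no parallel change. No contact with control CLCs is needed, because the records already exist. The cost is about 119 to 199 more reviewer hours at that maximum, an extension of the data-use amendment to control sites, and a rule against reviewing charts from one's own site.
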